#### **7.1.2.2 Full Physical Exam**

The investigator or qualified designee will perform a complete physical exam during the screening period. Clinically significant abnormal findings should be recorded as medical history. A full physical exam should be performed during screening,

### **7.1.2.3 Vital Signs**

The investigator or qualified designee will take vital signs at screening, prior to the administration of each dose of trial treatment and at treatment discontinuation as specified in the Trial Flow Chart (Section 6.0). Vital signs should include temperature, pulse, respiratory rate, weight and blood pressure. Height will be measured at screening only.

### **7.1.2.4 Eastern Cooperative Oncology Group (ECOG) Performance Scale**

The investigator or qualified designee will assess ECOG status (see Section 11.1) at screening, prior to the administration of each dose of trial treatment and discontinuation of trial treatment as specified in the Trial Flow Chart.

### **7.1.2.5 Tumor Imaging and Assessment of Disease**

Tumor imaging will be performed as outline in the flowchart under Section 6, typically every 8-16 weeks or as clinically indicated.

Radiologic recurrence/progression of disease should be confirmed 4-8 weeks after the initial scan and patients can continued treatment until confirmation if clinically stable and no other immediate reason for discontinuation is present.

Whenever possible clinical progression should be confirmed radiologically.

### **7.1.2.6 Tumor Tissue Collection and Correlative Studies Blood Sampling**

A minimum of 10 slides (from the original tumor prior to initiation of curative intent therapy) will be collected.

Blood will be obtained at baseline and at the time of the second treatment. Please see tissue/blood collection SOP provided separately.

## **7.2 Research Tests**

Tissue obtained (PRIOR to curative intent therapy) from the diagnostic biopsy/panendoscopy and/or during surgical resection, and whole blood samples (in PAXGene tubes).

The correlative work will be performed/coordinated at the University of Chicago, and may be done with collaborators e.g. at Incyte or Merck.

### **7.2.1 Sample Shipping**

All the tissue, whole blood and serum samples will be collected in the HTRC and additional details will be provided in a brief Tissue/Blood SOP that will be continually updated.

### **7.2.2 IHC staining**

→ Multicolor immunohistochemistry will be performed and results will be descriptive and presented in tabular with a focus on highlighting changes from pre- treatment samples.

Markers will include PD-L1 (research), and CD8.

Initial PD-L1 for allocation to a sample group will be done using the DAKO 22C3 CLIA assay for PD-L1 staining.

Additional staining for FOXP3, CD163, IDO, CD206, CD11a, CD163, and related markers if appropriate based on assay availability may be added.

### **7.2.3 Nanostring Analysis**

From 3-5 FFPE slides RNA will be extracted using the Qiagen RNA/DNA FFPE kit and protocol. A Nanostring probeset including ca 20-800 immune and other marker related probes will be used using the Nanostring (Seattle) standard ordering and analysis process. The Nanostring nCounter available in the [name] at the University of Chicago will be used. Alternatively FFPE based RNAseq libraries may be constructed using the Illumina FFPE RNA access protocol. The lab is experienced with both the Nanostring and FFPE RNAseq process and additional details are available on request. These are exploratory analyses. Specific processing information will be made available in a continually updated SOP for tissue collection and processing.

### **7.2.4 Tumor DNA Analysis**

Exome sequencing from tumor and normal blood white cells will be performed on the tumor samples for an exploratory analysis of correlation of genetic aberrations, immune phenotype and tumor response. In addition tumor RNAseq analysis will be performed from tumor tissue. Specific processing information will be made available in a continually updated SOP for tissue collection and processing.

### **7.2.5 Germline DNA analysis**

Blood will be obtained from all patients for exome sequencing of normal DNA (see above). Specific processing information will be made available in a continually updated SOP for tissue collection and processing.

### **7.2.6 RNA analysis from blood**

Blood samples will be obtained at baseline and after 3 weeks (administration of cycle 2 dose). Samples will be processed for RNA extraction (e.g. using the PAXgene RNA kit/tubes). RNA will be analysed by Nanostring (see above) or RNAseq) in an exploratory fashion comparing baseline with on-treatment inflammatory markers. Specific processing information will be made available in a continually updated SOP for tissue collection and processing.

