#### **4.3.1.2 Risk from Pembrolizumab**

An open-label Phase I study (Protocol 001) is being conducted to evaluate the safety and clinical activity of single agent pembrolizumab. The dose-escalation portion of this study evaluated 3 dose levels, 1 mg/kg, 3 mg/kg, and 10 mg/kg, administered every 2 weeks in subjects with advanced solid tumors. All 3 dose levels were well tolerated and no DLTs were observed. Based on pharmacokinetic (PK) data showing a half-life of 21 days, the Protocol was amended to include a dosing frequency of every 3 weeks in expansion cohorts. Of a total of 479 subjects, who have received pembrolizumab in Protocol 001, 466 (97.3%) experienced treatment-emergent AEs, of which 368 (76.8%) were considered drug-related. Serious AEs were reported in 30.1% of subjects, but SAEs that were attributed as potentially (possibly, probably, or definitely) drug-related by investigators were reported in 6.7% of subjects overall. Potential irAEs have been observed, including pneumonitis in both melanoma and NSCLC cohorts. The most commonly reported treatment-emergent AEs experienced have been fatigue, nausea, cough, pruritus, diarrhea, and rash. Most subjects continued treatment despite of AEs, and only 4.2% of subjects discontinued study treatment because of an AE that was considered related to study treatment by investigators. Thus, the overall AE summary suggests that pembrolizumab is generally tolerable, and AEs are generally manageable in subjects.

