### 5.1.3 Subject Exclusion Criteria

The subject must be excluded from participating in the trial if the subject:

1. Is currently participating and receiving study therapy or has participated in a study of an investigational agent and received study therapy or used an investigational device within 2 weeks of the first dose of treatment.

2. Has a diagnosis of immunodeficiency or is receiving systemic steroid therapy or any other form of immunosuppressive therapy within 7 days prior to the first dose of trial treatment.
3. Has a known history of active TB (Bacillus Tuberculosis)
4. Has hypersensitivity to pembrolizumab, epacadostat or any of its excipients.
5. Has had a prior anti-cancer monoclonal antibody (mAb) within 3 weeks prior to study Day 1, or targeted small molecule therapy within 2 weeks prior to study Day 1, or who has not recovered (i.e.,  $\leq$  Grade 1 or at baseline) from adverse events due to agents administered more than 4 weeks earlier.
6. Has not recovered from prior surgery, chemotherapy or radiation therapy from adverse events due to a previous treatment/ administered agent (i.e.,  $\leq$  Grade 1 or return to baseline prior to treatment).
  - Note: Subjects with  $\leq$  Grade 2 neuropathy, any grade hearing loss or tinnitus, or typical side effects from radiotherapy are an exception to this criterion and may qualify for the study.
  - Note: If subject received major surgery, they must have recovered adequately from the toxicity and/or complications from the intervention prior to starting therapy.
7. Has a known additional malignancy that is progressing or requires active treatment. Exceptions include basal cell carcinoma of the skin or squamous cell carcinoma of the skin that has undergone potentially curative therapy or in situ cervical cancer or any tumors that are not likely to influence live expectancy in the subsequent 3 years without active treatment (e.g. low grade prostate cancer in absence of therapy).
8. Has known active (=growing) central nervous system (CNS) metastases and/or carcinomatous meningitis. Radiation or resected brain metastasis are acceptable if clinically stable.

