## 6.0 TRIAL FLOW CHART

### 6.1 Study Flow Chart

Trial Period:	Screening Phase		Treatment Cycles *								End of Treatment (D/C)	Post-Treatment			
	Treatment Cycle/Title:	Pre-screening (Visit 1)	Main Study Screening (Visit 2)	1	2	3	4	To be repeated beyond 8 cycles **				Safety Follow-up	Follow Up Visits	Survival Follow-Up	
Scheduling Window (Days):		-28 to -1		± 3	± 3	± 3	± 3	± 3	± 3	± 3	± 3	At time of D/C	30 days post D/C	Every 8 weeks post D/C	Every 12 weeks
Administrative Procedures															
Informed Consent	X														
Inclusion/Exclusion Criteria	X	X													
Demographics and Medical History	X	X													
Prior and Concomitant Medication Review	X	X	X	X	X	X	X	X	X	X	X	X			
Trial Treatment Administration			X	X	X	X	X	X	X	X	X				
Post-study anticancer therapy status												X			
Survival Status												X	X	X	X
Clinical Procedures/Assessments															
Epacadostat administration (daily po)			X	X	X	X	X	X	X	X	X				
Pembrolizumab administration (iv q3 weeks)			X	X	X	X	X	X	X	X	X				
Review Adverse Events			X	X	X	X	X	X**	X	X**	X				
Full Physical Examination		X	X	X	X	X	X	X**	X	X**	X	X	X	X	
Vital Signs and Weight		X	X	X	X	X	X	X	X	X	X	X	X	X	
ECOG Performance Status		X	X	X	X	X	X	X**	X	X**	X	X	X	X	

Trial Period:	Screening Phase		Treatment Cycles*								End of Treatment	Post-Treatment			
	Treatment Cycle/Title:	Pre-screening (Visit 1)	Main Study Screening (Visit 2)	1	2	3	4	To be repeated beyond 8 cycles**				Discontinuation (D/C)	Safety Follow-up	Follow Up Visits	Survival Follow-Up
							5	6	7	8					
Scheduling Window (Days):		-28 to -1		± 3	± 3	± 3	± 3	± 3	± 3	± 3	± 3	At time of D/C	30 days post D/C	Every 8 weeks post D/C	Every 12 weeks
feasible															
Correlative Studies Blood Collection including a) germline DNA collection and b) PAXgene tube for RNA		X 		X 											

**1. The fresh biopsy/FNA requirement can be waived under extenuating circumstances after approval by the PI ([name]) e.g such a procedure is not safe or technically feasible.**

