### **7.2.6.1 Pharmacodynamic Evaluations**

#### **7.2.6.1.1 Blood Collection for RNA**

Blood will be collected at baseline, and at the time of 2nd administration of pembrolizumab. Details are provided in the Flow Chart and a brief SOP for tissue will be available and updated continually during the study period containing specific details (tube color, numbers, HTRC contact info etc).

No Pharmacokinetic evaluations will be done.

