#### **7.2.8.1 Screening period**

Screening period is 30 days prior to initiation of study drug. See flow chart under Section 6 for specific items.

Protocol #: UC IRB17-1539

Version Date: 1/23/2018

x All patients must have completed curative intent therapy for locally advanced HNSCC within 24 weeks prior to enrollment.

x Tissue must have been collected **PRIOR** to starting curative intent therapy on all patients (see eligibility criteria)

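### The baseline blood RNA tube is scheduled at screening, so it may be drawn before washout of prior therapy is complete; a pre-dose Cycle 1 Day 1 draw would be cleaner (low priority)

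*Combined protocol and SAP*

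**What the plan says.** Section 7.2.6 gives two time points: "Blood samples will be obtained at baseline and after 3 weeks (administration of cycle 2 dose"). The stated use is exploratory, "comparing baseline with on-treatment inflammatory markers". It gives no calendar day for baseline; nor do 7.1.2.6 and 7.2.6.1.1. The latter adds: "Details are provided in the Flow Chart and a brief SOP for tissue", and the SOP is not part of the documents.

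In the flow chart (6.1) the row is "Correlative Studies Blood Collection including a) germline DNA collection and b) PAXgene tube for RNA". It is marked at Main Study Screening with footnotes 2 and 3, blank at Cycle 1, and marked at Cycle 2 with footnote 3. Footnote 3 is the PAXgene tube, so the baseline RNA tube is a screening tube.

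The washouts in 5.1.3 are anchored later. Criterion 5, counting back from the first study day, excludes "prior anti-cancer monoclonal antibody (mAb) within 3 weeks prior to study Day 1, or targeted small molecule therapy within 2 weeks prior to study Day". Criterion 2 covers systemic steroids and "any other form of immunosuppressive therapy within 7 days prior to the first dose of trial treatment". Nothing ties the RNA draw to the end of either period.

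For pembrolizumab, 4.3.1.2 reports: "Based on pharmacokinetic (PK) data showing a half-life of 21 days".

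**The concern.** The comparison takes each patient as his or her own control, so the baseline should represent the state from which study treatment starts. The washouts bring patients to a common minimum time off prior therapy, but only by Day 1. A tube drawn at screening can catch a patient earlier on that path. Any change in inflammatory markers due to falling levels of a prior anti-PD-1/PD-L1 antibody, or to recovery from steroids, is then counted as change on pembrolizumab plus epacadostat.

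Cohort 2 makes this plausible: inclusion criterion 2b requires the last anti-PD-1/PD-L1 treatment to fall in the 6 weeks before the start. There is no control arm, and 7.2.6.1.1 rules out pharmacokinetic sampling, so neither a comparator nor a drug level could separate the two sources. A tube not drawn before the first dose cannot be replaced later.

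**Working it through.** **Inputs.**
- Washouts (5.1.3): monoclonal antibody 21 days, targeted small molecule 14 days, steroids or other immunosuppression 7 days.
- Half-life (4.3.1.2): 21 days.
- Cycle length (6.1): 21 days.
- Lead time from draw to Day 1: the documents disagree.
  - 5.1.2, and the text under Table 7 in 7.2.7: 10 days for screening laboratory tests. Table 7 lists correlative blood, so this window may cover the tube.
  - Note to 6.1: 14 days for screening laboratory tests.
  - Flow chart header: Day -28 to -1.
  - 7.2.8.1: "Screening period is 30 days prior to initiation of study drug".

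**Convention.** Day -n means n days before Day 1. A last antibody dose on Day -21 is taken as just meeting the washout.

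**Formulas**, for a draw L days before Day 1, washout W and last antibody dose on Day -D:
- time off therapy guaranteed by the washout at the draw = max(0, W - L)
- nominal interval to the Cycle 2 sample = L + 21 (before the ±3-day visit window)
- antibody remaining at the draw = 0.5^((D - L)/21)
- antibody remaining on Day 1 = 0.5^(D/21)

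**Time off therapy and interval.**

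| Draw | Antibody | Small molecule | Steroid | Interval to Cycle 2 |
|---|---|---|---|---|
| Day -1 | 20 d | 13 d | 6 d | 22 d |
| Day -10 | 11 d | 4 d | 0 d | 31 d |
| Day -14 | 7 d | 0 d | 0 d | 35 d |
| Day -28 | 0 d | 0 d | 0 d | 49 d |

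Section 5.6.3 bars antineoplastic therapy, immunotherapy and most systemic steroids during screening. A zero therefore does not mean treatment was continuing. It means that the last dose may have come just before screening opened, because no minimum gap is set.

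**Antibody remaining.**
- D = 21, L = 1: 0.5^(20/21) = 0.52 at the draw, against 0.5^(21/21) = 0.50 on Day 1.
- D = 21, L = 10: 0.5^(11/21) = 0.70, against 0.50. Under the ban in 5.6.3 this needs screening to open after Day -21.
- D = 29, L = 28: 0.5^(1/21) = 0.97, against 0.5^(29/21) = 0.38. This patient meets the 21-day washout and the Cohort 2 limit of 42 days.

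**What this does to the exposure contrast.** Assume a single prior dose equivalent to the study dose, first-order decay, and a Cycle 2 sample taken before the infusion. In units of one dose, exposure at Cycle 2 is 0.5^((D + 21)/21) + 0.5.
- D = 21: Cycle 2 exposure is 0.25 + 0.50 = 0.75. From a Day -10 draw it goes from 0.70 to 0.75, a rise of 0.05. From a Day 1 draw it goes from 0.50 to 0.75, a rise of 0.25.
- D = 29: Cycle 2 exposure is 0.19 + 0.50 = 0.69. From a Day -28 draw it falls, 0.97 to 0.69. From a Day 1 draw it rises, 0.38 to 0.69.

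**The case against.** The strongest reply is that early sampling is permitted, not prescribed. A site that draws on Day -1, or a patient whose prior therapy ended long ago, loses almost nothing (0.52 against 0.50). If the 10-day laboratory window governs this tube, the Day -28 example cannot occur and the interval is 22 to 31 days. The SOP may narrow the timing further, and the extracted flow chart is broken in places, so neither can be fully checked. All of this stands. It reduces the problem but does not close it: at Day -10 the washouts guarantee only 11 days off an antibody and 4 off a small molecule, and the steroid washout has not begun.

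It is also fair that these figures describe residual drug, not RNA. The documents give no link from antibody level to marker change, so no bias in the markers can be computed. Carry-over also belongs to this population: up to about 50% of a prior antibody dose can remain even on Day 1.

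Some stronger readings are tempting and not supported:
- A reader might see a contradiction between the 3 weeks in 7.2.6 and the longer gap between samples. With 21-day cycles, the phrase more naturally times the Cycle 2 dose from the start of treatment.
- A reader might take blood RNA as the only measure of on-treatment change. Section 7.2.2 also plans immunohistochemistry looking at change from pre-treatment tissue, and 4.2.3 allows an optional on-treatment biopsy.
- A reader might infer a systematic difference between cohorts. Cohort 1 has no rule on how recent the last anti-PD-1/PD-L1 dose was, so it may or may not differ, and no cohort comparison of blood RNA is planned.

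**Conclusion.** The point holds as a possibility that the schedule leaves open. The baseline RNA tube may be drawn before washout is complete, under every screening window the documents give. The effect runs from negligible (a draw near Day -1) through 70% against 50% of a prior antibody dose (Day -10) to 97% against 38% (Day -28). These figures rest on the stated 21-day half-life applied to the prior antibody, on patients who sit near the eligibility limits, and on reading the flow chart columns as described.

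A reader might infer that every baseline sample is contaminated, or that the 97% figure is typical. The documents support neither. The consequence is confined to an exploratory comparison: response rate, the two-stage rule, sample size, survival and safety are untouched. Low priority, but worth doing because the change is so cheap.

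**What to change.** In 6.1, 7.1.2.6, 7.2.6 and 7.2.6.1.1:
- Define the baseline PAXgene tube (footnote 3) as drawn on Cycle 1 Day 1 before the first dose of either drug. Both drugs start that day, so both should be named.
- Leave the germline DNA tube (footnote 2) at screening.
- State that the Cycle 2 tube is drawn before that day's infusion. Section 5.3.6 already implies this by placing treatment after the day's procedures, so it is a clarification.
- Record with each sample its date and the date of last prior therapy, by class, so that remaining carry-over can be described or adjusted for.

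Separately, reconcile the 10-, 14-, 28- and 30-day screening windows and say which of them applies to correlative blood.

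Cost: the same tubes and number of draws, at a visit that already takes place. RNA kit handling moves to Day 1. The gain is a sample-to-sample interval of about 21 days (±3) for everyone, with all washouts met at baseline. It reduces carry-over but does not remove it.

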### **7.2.7 Laboratory Procedures/Assessments**

Details regarding specific laboratory procedures/assessments to be performed in this trial are provided below under Laboratory Safety Evaluations (Hematology, Chemistry and Urinalysis)

Laboratory tests for hematology, chemistry, urinalysis, and others are specified in Table 7.

**Table 7 Laboratory Tests**

Hematology	Chemistry	Urinalysis	Other
Hematocrit	Albumin	Blood	Serum $\beta$ -human chorionic gonadotropin†
Hemoglobin	Alkaline phosphatase	Glucose	( $\beta$ -hCG)†
Platelet count	Alanine aminotransferase (ALT)	Protein	PT (INR)
WBC (total and differential)	Aspartate aminotransferase (AST)	Specific gravity	aPTT
Red Blood Cell Count	Lactate dehydrogenase (LDH)	Microscopic exam ( If abnormal )	Total triiodothyronine (T3)
Absolute Neutrophil Count	Carbon Dioxide ‡	results are noted	Free tyroxine (T4)
Absolute Lymphocyte Count	( CO2 or bicarbonate )	Urine pregnancy test †	Thyroid stimulating hormone (TSH)
	Uric Acid		PK
	Calcium		
	Chloride		Blood for correlative studies
	Glucose		
	Phosphorus		
	Potassium		
	Sodium		
	Magnesium		
	Total Bilirubin		
	Direct Bilirubin ( If total bilirubin is elevated above the upper limit of normal )		
	Total protein		
	Blood Urea Nitrogen		

† Perform on women of childbearing potential only. If urine pregnancy results cannot be confirmed as negative, a serum pregnancy test will be required.  
‡ If considered standard of care in your region.

Protocol #: UC IRB17-1539

Version Date: 1/23/2018

Laboratory tests for screening or entry into the Second Course Phase should be performed within 10 days prior to the first dose of treatment. After Cycle 1, pre-dose laboratory procedures can be conducted up to 72 hours prior to dosing. Results must be reviewed by the investigator or qualified designee and found to be acceptable prior to each dose of trial treatment.

### **7.2.6.1 Pharmacodynamic Evaluations**

#### **7.2.6.1.1 Blood Collection for RNA**

Blood will be collected at baseline, and at the time of 2nd administration of pembrolizumab. Details are provided in the Flow Chart and a brief SOP for tissue will be available and updated continually during the study period containing specific details (tube color, numbers, HTRC contact info etc).

No Pharmacokinetic evaluations will be done.

### **7.2.7 Other Procedures**

#### **7.2.7.1 Withdrawal/Discontinuation**

When a subject discontinues/withdraws prior to trial completion, all applicable activities scheduled for the final trial visit should be performed at the time of discontinuation. Any adverse events, which are present at the time of discontinuation/withdrawal should be followed in accordance with the safety requirements outlined in Section 7.2 - Assessing and Recording Adverse Events. Subjects who a) attain a CR or b) complete 24 months of treatment with pembrolizumab may discontinue treatment with the option of restarting treatment if they meet the criteria specified in Section 7.1.5.5. After discontinuing treatment following assessment of CR, these subjects should return to the site for a Safety Follow-up Visit (described in Section 7.1.5.3.1) and then proceed to the Follow-Up Period of the study (described in Section 7.1.5.4).

#### **7.2.7.2 Blinding/Unblinding**

There is no blinding in this study.

### **7.2.8 Visit Requirements**

Visit requirements are outlined in Section 6.0 - Trial Flow Chart. Specific procedure-related details are provided above in Section 7.1 - Trial Procedures.

#### **7.2.8.1 Screening period**

Screening period is 30 days prior to initiation of study drug. See flow chart under Section 6 for specific items.

Protocol #: UC IRB17-1539

Version Date: 1/23/2018

x All patients must have completed curative intent therapy for locally advanced HNSCC within 24 weeks prior to enrollment.

x Tissue must have been collected **PRIOR** to starting curative intent therapy on all patients (see eligibility criteria)

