## 2.2 Trial Diagram

Recurrent/metastatic head and neck cancer with prior/ongoing anti-PD-1/anti-PD-L1 treatment

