## 4.2 Rationale

### 4.2.1 Rationale for combining PD-1 blockade with IDO inhibition in HNSCC.

IDO1 is a negative regulatory mechanism that contributes to tumor-derived immune suppression. In preclinical models, IDO1 inhibition has been shown to synergize with blockade of anti-PD-1/PD-L1 in delaying tumor growth and increasing OS (*Holmgaard 2013, Spranger 2013*). This effect was shown to be T-cell dependent, leading to enhanced T-cell proliferation and interleukin-2 production within the tumor and to a **marked increase in the effector-to-regulatory T cell ratios in the tumors**.

Epacadostat represents a novel, potent, and selective inhibitor of the enzyme indoleamine 2,3 dioxygenase 1 (IDO1) in both human tumor cells and human dendritic cells (DCs). For a thorough discussion of the pharmacology of epacadostat, refer to the epacadostat Investigator's Brochure ([iIB](#)).

While the majority of such patients with HNC can be treated with curative intent using multimodality approaches, a significant fraction of patients will fail therapy (typically within 12-18 months), especially those patients with high risk features such as advanced/bulky nodal stage, non-response to induction chemotherapy, residual disease on salvage surgery, and HPV-negative status.

HNSCC shows some of the highest levels of a CD3+/8+ lymphocyte infiltration (TILs), and T-cell inflammation, and multiple immune escape mechanisms are present (*Saloura/Seiwert, ASCO 2014, Lyford-Pike 2013*). PD-L1 expression is prominent in up to 70% of tumors, and similarly to other cancer type (*Powderly 2013*) correlates with response in the Keynote 12 study (*Seiwert, ASCO 2014/2015*) as well as a smaller cohort using the anti-PD-L1 antibody MEDI4636 (*Gibson ASCO 2015*).

Since pembrolizumab has shown significant single agent activity in HNC with a response rate of 16-18% (*Seiwert Lancet Oncology 2016; Chow JCO 2016*), excellent tolerability, and potentially affords long-term survival in a fraction of patients, further study of pembrolizumab, in particular combination aimed at overcoming acquired resistance or suboptimal benefit are indicated and clinically relevant.

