## **5.0 METHODOLOGY**

### **5.1 Entry Criteria / Eligibility**

#### **5.1.1 Diagnosis/Condition for Entry into the Trial**

#### **5.1.2 Subject Inclusion Criteria**

In order to be eligible for participation in this trial, the subject must fulfill the following entry criteria:

1. Patients must have histologically confirmed squamous cell carcinoma of the head and neck (unresectable and not amenable to curative intent therapy)
2. Meet criteria for either the Acquired Resistance OR the Suboptimal Benefit Cohort
  - a. **Acquired Resistance is defined as (i and ii must both be met):**
    - i. **Prior *benefit* from anti-PD-1/PD-L1 therapy defined as a) prior response, *and/or* b)  $\geq 5$  months of stable disease (SD). Intervening therapies are allowed.**
    - ii. **Progressive Disease (PD) on recent scans**
  - b. **Suboptimal Benefit is defined as (i and ii must both be met):**
    - i. **Prolonged stable disease  $\geq 5$  months OR Suboptimal response ( $>10\%$  &  $<50\%$  shrinkage per RECIST at any evaluation timepoint)**
    - ii. **Ongoing stable disease on recent scans**
    - iii. **Last treatment with an anti-PD-1/PD-L1 agent within 6 weeks prior to starting protocol treatment**
3. Archival tissue for PD-L1 staining (alternatively a new biopsy (core) at baseline can be used). A minimum of 10 slides is required (unless approval from the PI is obtained)
4. Measurable disease per RECIST 1.1.
5. Known HPV status
6. ECOG performance status 0 or 1
7. Be willing and able to provide written informed consent/assent for the trial.
8. Be  $\geq 18$  years of age on day of signing informed consent.
9. Demonstrate reasonable organ function as defined in
10. Table 1, all screening labs should be performed within 10 days of treatment initiation.

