#### **Primary Outcome: Response rate**

Clinical and pathologic response rates will be determined and 90% confidence intervals obtained using the exact binomial distribution.

A Simon's two-stage design (Simon, 1989) will be used – using the Minimax variant - for both cohorts. The null hypothesis that the true response rate is 3% [ $p_0$ ] (*assuming poor efficacy of e.g. pembrolizumab treatment in patients, who have failed prior PD-1/PD-L1 therapy*) will be tested against a one-sided alternative. In the first stage, 10 [ $n_1$ ] patients will be accrued. If there are no responses [ $r_1$ ] in these 10 [ $n_1$ ] patients, the study will be stopped.

Otherwise, 5 additional patients will be accrued for a total of 15 [ $n$ ] patients. The null hypothesis will be rejected if 2 or more responses are observed in 15 patients. This design yields a type I error rate of 0.0667 and 80% power when the true response rate is 20%.

A response rate of 20% would be considered clinically meaningful for HNC in the absence of alternative treatment options in the 2nd/3rd line setting (after PD-1/PD-L1 failure) and further development of pembrolizumab + epacadostat would proceed.

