## 10.6 Registration

Prior to registration and any study-specific evaluations being performed, all patients must have given written informed consent for the study and must have completed the pre-treatment evaluations. Patients must meet all of the eligibility requirements listed above. Study coordinators will register patients. This study is intended as a single center study performed at the University of Chicago.

When registering a subject, the following must occur:

- Confirm that a current IRB approval letter for the correct version of protocol/consent and has an annual update on file, if appropriate.
- Submit all required materials (Eligibility Checklist, Source documentation, & signed consent form) to confirm eligibility and required pre-study procedures to the CRA a minimum of 48 hours prior to the subject's scheduled therapy start date.
- Source documentation includes copies of all original documents that support each inclusion/exclusion criteria. The eligibility checklist does not serve as source documentation but rather as a checklist that original source documentation exists for each criterion.
- Communicate with the CRA to ensure all necessary supporting source documents are received and the potential subject is eligible to start treatment on schedule. If there are questions about eligibility, the CRA will discuss it with the PI. PI may clarify, but not overturn, eligibility criteria.
- Affiliate sites must confirm registration of subjects by obtaining a subject study ID number from the CRA via phone, fax or email.
- If a subject does not start on the scheduled day 1 treatment date, promptly inform the CRA as the delay in start may deem the subject ineligible and/or require further or repeat testing to ensure eligibility.

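### Section 7.2.8.1 imposes a 24-week curative-therapy limit and a pre-curative tissue rule that are absent from the eligibility criteria, and the 24-week limit conflicts with the population defined there

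*Combined protocol and SAP*

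**What the plan says.** Section 7.2.8.1 (Screening period) has two bullets worded as requirements for everyone.

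- Prior therapy: "All patients must have completed curative intent therapy for locally advanced HNSCC within 24 weeks prior to enrollment".
- Tissue: it must have been collected before that therapy, with a pointer to the eligibility list: "to starting curative intent therapy on all patients (see eligibility criteria".

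The population is defined elsewhere.

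- Section 2.2 describes it as "Recurrent/metastatic head and neck cancer with prior/ongoing anti-PD-1/anti-PD-L1 treatment".
- Section 5.1.2 requires unresectable disease that is beyond curative treatment. Cohort 1 needs an earlier response or at least 5 months of stable disease on anti-PD-1/PD-L1 therapy, then progression; treatment in between is permitted. Cohort 2 needs at least 5 months of stable disease, or shrinkage of more than 10% and less than 50%, with disease still stable. Cohort 2 also carries a recency condition: "Last treatment with an anti-PD-1/PD-L1 agent within 6 weeks prior to starting protocol treatment".
- On tissue, 5.1.2 asks for "Archival tissue for PD-L1 staining (alternatively a new biopsy (core) at baseline can be used". Section 4.2.3 makes a baseline biopsy mandatory when no archival tissue exists. Sections 7.1.2.6 and 7.2, by contrast, repeat the pre-curative condition.

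**The concern.** The tissue bullet relies on eligibility criteria that do not contain it, and the 24-week bullet has no counterpart there either. Two sections therefore give different answers to who may be enrolled.

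If 7.2.8.1 were enforced, the enrolled population would differ from the one in 5.1.2. The 3% null and 20% target response rates in 8.1 would then describe a different group of patients. If it were ignored, patients would be enrolled against a written requirement. Section 10.5 sends all departures from the protocol to the IRB, and 10.6 lets the PI clarify eligibility criteria but not override them. Section 10.6 also says "Patients must meet all of the eligibility requirements listed above", which can be read to reach 7.2.8.1.

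**Working it through.** **1. The plan's own design figures.** For each cohort, 8.1 gives n1 = 10, stop at 0 responses, n = 15, reject at 2 or more. The rejection probability is P(X1 ≥ 2) + P(X1 = 1) × [1 − (1 − p)^5], where X1 is binomial(10, p).

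- p = 0.03: P(X1 = 0) = 0.97^10 = 0.7374; P(X1 = 1) = 10 × 0.03 × 0.97^9 = 0.2281; P(X1 ≥ 2) = 0.0345; 1 − 0.97^5 = 0.1413. Result: 0.0345 + 0.2281 × 0.1413 = 0.0667, as stated.
- p = 0.20: P(X1 = 0) = 0.1074; P(X1 = 1) = 0.2684; P(X1 ≥ 2) = 0.6242; 1 − 0.8^5 = 0.6723. Result: 0.6242 + 0.2684 × 0.6723 = 0.805, against a stated 80%.

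The design reproduces, and none of its inputs depends on 7.2.8.1.

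**2. The two lists side by side.**

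| Item | 5.1.2 / 5.1.3 | 7.2.8.1 |
|---|---|---|
| Earlier curative-intent therapy | not required | required of all |
| Time since that therapy | no limit | at most 24 weeks |
| Tissue | archival, or a new baseline core | from before curative therapy |

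The first row is enough for a contradiction. A patient who never had curative-intent therapy can meet every criterion in 5.1.2 and 5.1.3 and still fails 7.2.8.1. No assumption about treatment order is needed.

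**3. How tight the 24 weeks are on the stable-disease route.** Two assumptions are needed, and the documents state neither: (a) anti-PD-1/PD-L1 therapy began after curative therapy ended; (b) stable disease is counted from the start of anti-PD-1/PD-L1 therapy.

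- Limit: 24 × 7 = 168 days (168 / 30.44 = 5.5 months).
- Five months: 5 × 30.44 = 152.2 days, or 21.7 weeks.
- Remainder: 168 − 152.2 = 15.8 days, or 2.3 weeks.
- By calendar, five consecutive months run 150 to 153 days, leaving 18 to 15 days. With 4-week months, 5 × 28 = 140 days, leaving 28.

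In that remainder the patient must recur and start anti-PD-1/PD-L1 therapy. In Cohort 1, progression and any treatment in between must fit as well.

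**4. How firm assumption (a) is.** Section 2.2 supports it, as does 8.1, which refers to the "line setting (after PD-1/PD-L1 failure) and further development of pembrolizumab + epacadostat would proceed". Neither says when curative therapy was given. If the Cohort 2 recency condition is binding, anti-PD-1/PD-L1 therapy given wholly before curative therapy would leave at most 6 weeks for the entire curative course. Concurrent use is not ruled out.

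**5. Routes that cannot be sized.** Response (Cohort 1) and partial shrinkage (Cohort 2) carry no minimum duration. A patient who recurred early and responded quickly could meet both sections.

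**6. Tissue.** Pre-curative slides satisfy both sets of rules. The conflict arises when such tissue is lacking and a fresh baseline biopsy or post-treatment tissue is supplied. A baseline biopsy cannot predate a curative course that 7.2.8.1 says is already complete.

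**The case against.** The best defense is that sites will screen from Section 5.1. Sections 5.4, 7.1.1.2 and 7.2.8.2 all point to the inclusion and exclusion criteria. The registration checklist in 10.6 is built on those criteria, and its reference to eligibility requirements most naturally means the lists in 5.1. This stands as a reason to expect limited practical effect. It does not remove two mandatory sentences that disagree with those lists.

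On tissue, 5.1.2 lets the PI accept fewer slides, and a flow-chart footnote lets the PI waive the fresh biopsy. Sections 7.1.2.6 and 7.2 describe collection rather than eligibility. These points narrow the tissue conflict but do not resolve it. The flow-chart row tied to that footnote is incomplete in the text available, so part of the tissue schedule could not be checked.

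Stronger readings are tempting but not supported:

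- A reader might infer that the 24-week rule shuts out most of the intended patients. No figure in the documents gives a share, and the response and shrinkage routes stay open.
- A reader might set the limit against 4.2.1, where "a significant fraction of patients will fail therapy (typically within 12-18 months". The word within makes that an upper bound, so failures before 24 weeks are included. The sentence also concerns head and neck cancer patients treated with curative intent in general, and it does not say when its clock starts.
- A reader might conclude that the bullets were carried over from an adjuvant protocol, because 4.2.4.2 speaks of adjuvant therapy. That is plausible, but it remains an inference.
- The page carrying 7.2.8.1 has a footer dated 1/23/2018, while early sections carry 04/24/2019. That does not show the text is superseded; it stands in the body of the protocol.

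**Conclusion.** The contradiction holds and should be corrected. Its firm core is that 7.2.8.1 sets two universal requirements missing from 5.1.2 and 5.1.3, and that a patient never treated with curative intent is treated differently by the two sections.

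The 16-day margin (15 to 18 by calendar, 28 with 4-week months) is illustrative. It applies to the stable-disease route only and rests on assumptions (a) and (b). The share of intended patients affected cannot be quantified. The tissue conflict is secondary: it is limited to patients without pre-curative tissue and to exploratory objectives.

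The statistical design is not at fault. What is at stake is which patients the design's response rates refer to, and whether enrollment under 5.1.2 is recorded as a departure from the protocol.

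**What to change.** Reconcile 7.2.8.1 with 5.1.2 and 5.1.3 so that a single eligibility list governs.

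- Remove the two bullets from 7.2.8.1, unless the sponsor confirms that a limit on time since curative therapy is intended. In that case, write the limit into 5.1.2 and make it compatible with both cohort definitions, including patients who never had curative therapy.
- Align the tissue wording in 7.1.2.6 and 7.2 with 5.1.2 and 4.2.3, so that archival or fresh baseline tissue is accepted throughout.
- The adjuvant wording in 4.2.4.2 is a separate matter, but it could be checked in the same edit.

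The cost is one wording amendment with IRB review. Endpoints, sample size and the two-stage rule stay as they are. The one consequence to accept knowingly is that removing the first bullet leaves no limit on time since curative therapy.
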